7.5. Preparation/Handling/Storage/Accountability

All prexasertib should be refrigerated.

Prexasertib will be administered as an IV infusion using a central or peripheral IV line and will be filtered through an in-line filter. Prexasertib should be handled according to standard procedures and precautions consistent with a cytotoxic anticancer drug.

The dosage strength of 67-mg prexasertib lactate monohydrate drug product will be used in Study JTJN. The vial will contain a slight excess to facilitate the withdrawal of the labeled amount 67 mg/vial for use with an appropriate device, such as an infusion set. Reconstituting the vial contents with water for injection yields a clear yellow solution with a concentration of 3.3 mg/mL of prexasertib.

For the most current detailed formulation information and preparation instructions, refer to the IB and Pharmacy Binder.

7.6. Treatment Compliance

The study medication will be administered only at the investigational sites by the authorized study site personnel. As a result, treatment compliance is ensured.

7.7. Concomitant Therapy

Except as noted, no other chemotherapy, immunotherapy, cancer-related hormone therapy, herbal drugs, or experimental drugs will be permitted while the patients are on study treatment. Patients on stable doses of bisphosphonates or RANK-L targeted agents (for example, denosumab) are allowed to continue. These agents should not be initiated within the 2 weeks prior to study enrollment or at any point while on the study. Replacement hormonal therapy or tamoxifen or aromatase inhibitors initiated before study entry will be allowed.

Radiotherapy (including palliative radiotherapy) will only be permitted if it is agreed upon by both the investigator and the Lilly CRP/CRS. If the lesion that is to be treated is a target lesion, the lesion will be censored at the time of treatment. However, the patient may be eligible to remain on study drug treatment provided there are other lesions that can be followed for progression. Treatment delays of prexasertib may be required if radiotherapy is administered.

In addition, any disease progression requiring other forms of specific antitumor therapy will necessitate discontinuation from study treatment.

Patients should receive full supportive care during the trial. Guidelines from ASCO (Smith et al. 2015) should be followed for patients requiring support with G-CSF. Primary or secondary

prophylactic G-CSF support is permitted at the discretion of the investigator. Primary prophylaxis with G-CSF starting in the first cycle and continuing through subsequent cycles of chemotherapy is recommended in patients who have an approximately 20% or higher risk for febrile neutropenia on the basis of patient-, disease-, and treatment-related factors. As outlined in the ASCO guidelines, the following factors may be relevant to the JTJN patient population and should be considered when estimating the patient's overall risk of febrile neutropenia: Age ≥ 65 , advanced disease, previous chemotherapy or radiation therapy, poor nutritional status, cardiovascular disease, or multiple comorbid conditions. It is recommended that prophylactic short-acting G-CSF be initiated within 24-72 hours of study drug administration and continued through post-nadir recovery (Crawford et al. 2010). It is recommended that long-acting G-CSFs, such as pegfilgrastim, be administered the day after treatment (Crawford et al. 2017). Per NCCN guidelines, Phase 2 data support the use of pegfilgrastim in regimens with a 2-week cycle, with uniform consensus that this is appropriate (Category 2A) (Crawford et al. 2017).

Prophylactic antibiotics may be considered for use in patients who have experienced neutropenic fever or patients deemed at higher risk for neutropenic fever by the investigators. The treatment should be consistent with ASCO guidelines (Flowers et al. 2013).

Erythropoietin and packed RBC transfusion may be used according to ASCO guidelines (Rizzo et al. 2008) if clinically indicated at any time during the study. Patients who are stable on erythropoietin for >1 month before study entry may continue their treatment.

On days when prexasertib is administered, patients should avoid taking multiple (>1) concomitant medications that are known or suspected to cause prolonged QTc or Torsades de Pointes and, if possible, alternative agents should be considered. In addition, at the start of the study and on days when prexasertib is administered, care should be taken to ensure that serum electrolyte levels are within the normal range.

[figure not shown]
Strong P-gp and BCRP inhibitors (e.g., amiodarone, carvedilol, clarithromycin, dronedarone, itraconazole, propafenone, quinidine, ranolazine, verapamil, cyclosporine A, or eltrombopag) should be used with caution, as prexasertib is a substrate of both P-gp and BCRP.

7.8. Treatment after the End of the Study

Patients who are still on prexasertib at the time of study completion may continue to receive prexasertib if they are experiencing clinical benefit and no undue risks. The continued access period will apply to this study only if ≥ 1 patient is still on prexasertib when study completion occurs. Lilly will notify investigators when the continued access period begins. Lilly may allow patients to enroll in a "rollover" protocol to provide long-term continued access for patients enrolled in this study.

The continued access period will begin after study completion and ends at End of Trial (Figure JTJN.7.1). The patient's continued access to prexasertib will end when a criterion for discontinuation is met (Section 8). Continued access follow-up will begin the day after the patient and the investigator agree to discontinue prexasertib and lasts approximately 30 (± 7)

days. Follow-up procedures will be performed as shown in the Continued Access Schedule of Activities [Table JTJN.3](#).

^a Lilly will notify sites when the continued access period begins and ends.

^b Study completion occurs after the clinical trial database is locked and the final analysis of the primary and secondary endpoints have been performed. Lilly will notify sites when study completion occurs.

^c End of study occurs at the last visit or last scheduled procedure for the last patient.

Figure JTJN.7.1. Continued access diagram.

Patients who are in short-term follow-up when the continued access period begins will continue in short-term follow-up until the 30-day short-term follow-up visit is completed. Long-term follow-up does not apply.

Patients who are in long-term follow-up when the continued access period begins will be discontinued from long-term follow-up.

8. Discontinuation Criteria

8.1. Discontinuation from Study Treatment

Patients will be discontinued from study treatment in the following circumstances:

- the patient is enrolled in any other clinical study involving an investigational product or any other type of medical research judged not to be scientifically or medically compatible with this study
- the patient becomes pregnant during the study
- the patient is significantly noncompliant with study procedures and/or treatment
- disease progression
- unacceptable toxicity
- the patient, for any reason, requires treatment with another therapeutic agent that has been demonstrated to be effective for treatment of the study indication. Discontinuation from prexasertib will occur prior to introduction of the new agent
- the investigator decides that the patient should be discontinued from prexasertib
- the patient requests to be discontinued from prexasertib
- the patient's designee (legal representative) requests that the patient be discontinued from prexasertib.

Patients who are discontinued from prexasertib will have follow-up procedures performed as shown in the Schedule of Activities (Section 2).

8.1.1. *Discontinuation of Inadvertently Enrolled Patients*

If Lilly or the investigator identifies a patient who did not meet enrollment criteria and was inadvertently enrolled, a discussion must occur between the Lilly CRP/CRS and the investigator to determine if the patient may continue in the study. If both agree it is medically appropriate to continue, the investigator must obtain documented approval from the Lilly CRP/CRS to allow the inadvertently enrolled patient to continue in the study. Patients who are discontinued from prexasertib will have follow-up procedures performed as shown in the Schedule of Activities (Section 2).

8.2. Discontinuation from the Study

Patients will be discontinued from the study in the following circumstances:

- the investigator or Lilly, for any reason, but considering the rights, safety and well-being of the patient(s) and in accordance with International Council for Harmonization (ICH)/Good Clinical Practice (GCP) Guidelines and local regulations, stops the study or stops the patient's participation in the study.
- the patient becomes pregnant during the study. See Section 9.2.1 regarding regulatory reporting requirements on fetal outcome.

- the investigator decides that the patient should be discontinued from the study:
- the patient requests to be discontinued from the study:
- the patient's designee (legal representative) requests that the patient be discontinued from the study.

The study will be discontinued if Lilly judges it is necessary for medical, safety, regulatory, or other reasons consistent with applicable laws, regulations, and GCP. Prior to discontinuation, the Ethical Review Board (ERB) (which approved the trial) will be notified according to local regulation.

Patients who are discontinued from the study will have follow-up procedures performed as shown in the Schedule of Activities (Section 2).

8.3. Lost to Follow-Up

A patient will be considered lost to follow-up if he or she repeatedly fails to return for scheduled visits and is unable to be contacted by the study site. Study site personnel are expected to make diligent attempts to contact patients who fail to return for a scheduled visit or who the site is otherwise unable to follow-up.

Study site personnel, or an independent third party, will attempt to collect the survival status for all enrolled patients who are lost to follow-up, including enrolled patients who do not receive prexasertib, within legal and ethical boundaries. Public sources may be searched for survival status information. If the patient's survival status is determined, the survival status will be documented, and the patient will not be considered lost to follow-up.

Lilly personnel will not be involved in any attempts to collect survival status information.

9. Study Assessments and Procedures

Section 2 provides the Schedule of Activities for this study.

Appendix 2 provides a list of the laboratory tests that will be performed for this study.

Appendix 4 provides the schedule for collection of PK samples in this study.

Unless otherwise stated in the following subsections, all samples collected for specified laboratory tests will be destroyed within 60 days after receipt of confirmed test results. Certain samples may be retained for a longer period, if necessary, to comply with applicable laws, regulations, or laboratory certification standards.

9.1. Efficacy Assessments

Tumor assessments, including tumor markers, will be performed for each patient at the times shown in the Schedule of Activities (Section 2).

Computed tomography (CT) scans, including spiral CT, are the preferred methods of measurement (CT scan thickness recommended to be ≤ 5 mm); however, magnetic resonance imaging (MRI) is also acceptable in certain situations, such as when body scans are indicated or if there is a concern about radiation exposure associated with CT. Intravenous and oral contrast is required unless medically contraindicated.

The CT portion of a positron emission tomography (PET)-CT scan may be used as a method of response assessment if the site can document that the CT is of identical diagnostic quality to a diagnostic CT (with intravenous and oral contrast). A PET scan alone or as part of a PET-CT may be performed for additional analyses but cannot be used to assess response according to RECIST 1.1 (Eisenhauer et al. 2009).

The method of tumor assessment used at baseline must be used consistently throughout the study. Radiologic scan of the thorax, abdomen, and pelvis is required. As an independent review of all or a subset of radiographic imaging scans may be conducted, copies of scans will be collected throughout the study and stored by a coordinating vendor designated by Lilly.

See Section 10.3.1 for definitions of the efficacy endpoints.

9.1.1. Appropriateness of Assessments

The measures used to assess safety and efficacy in this study is consistent with those used in most conventional oncology studies.

9.2. Adverse Events

The investigator should provide adverse event (AE) verbatim terms and then the terms will be mapped by Lilly or its designee to corresponding terminology within the Medical Dictionary for Regulatory Activities (MedDRA) Lower Level term (LLT) dictionary. The investigator will use Common Terminology Criteria for Adverse Events (CTCAE) version 4.0 to assign AE severity grades.

Investigators are responsible for:

- monitoring the safety of patients in this study and for alerting Lilly or its designee to any event that seems unusual, even if this event may be considered an unanticipated benefit to the patient
- the appropriate medical care of patients during the study
- documenting their review of each laboratory safety report
- following (through an appropriate health care option) AEs that are serious or otherwise medically important, considered related to study treatment or the study, or that caused the patient to discontinue prexasertib before completing the study. The patient should be followed until the event resolves, stabilizes with appropriate diagnostic evaluation, or is reasonably explained. Frequency of follow-up evaluation is left to the discretion of the investigator.

Lack of drug effect is not an AE in clinical studies, because the purpose of the clinical study is to establish treatment effect.

After the ICF is signed, study site personnel will record via case report form (CRF)/electronic data entry the occurrence and nature of each patient's preexisting conditions, including clinically significant signs and symptoms of the disease under treatment in the study. In addition, study site personnel will record via CRF/electronic data entry any change in the preexisting conditions and any new conditions as AEs. Investigators should record their assessment of the potential relatedness of each AE to study procedure or study treatment via CRF/electronic data entry.

The investigator will interpret and document whether or not an AE has a reasonable possibility of being related to study treatment or a study procedure, taking into account the disease, concomitant treatments, or pathologies. A "reasonable possibility" means that there is a cause and effect relationship between the study treatment and/or study procedure and the AE.

Adverse event grading of toxicities related to estimated glomerular filtration rate (GFR) should be evaluated based on the Cockcroft-Gault method or measured GFR ([Appendix 6](#)).

Planned surgeries and nonsurgical interventions should not be reported as AEs unless the underlying medical condition has worsened during the course of the study.

Study site personnel must report any dose modifications or treatment discontinuations that result from AEs to Lilly or its designee via CRF/electronic data entry, clarifying, if possible, the circumstances leading to the dose modification or discontinuation of treatment.

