Tumor Assessment	Radiologic imaging according to RECIST version 1.1	X	X	Perform approximately every 8 weeks (±1 week) up to 1 year, thereafter every 12 weeks (±1 week) by the same method used at baseline and throughout the study, until the patient has documented disease progression, starts another therapy, or study completion. The same method of imaging used at baseline should be used for each subsequent assessment. Scans should also be obtained as clinically indicated.
	Tumor measurement (palpable or visible)	X		
Adverse Events Collection/ CTCAE Grading		X	X	CTCAE version 4.0; for visit 801: includes hospitalizations, emergency department visits, and/or occurrence of SBO. After Visit 801, only study treatment-related serious events are to be reported.
Concomitant Medication Notation		X		Includes transfusions (platelets and RBCs) and information on over-the-counter and prescription analgesics use.
Laboratory/ Diagnostic Tests	Hematology	X		See Appendix 2 .
	Chemistry	X		See Appendix 2 .
	CA-125	X	X	Collect approximately every 8 weeks (±1 week) up to 1 year, thereafter every 12 weeks (±1 week) at same time as radiologic imaging (+/- 3 days), until the patient has documented disease progression, starts another therapy, or study completion.
	ECG	X		
	Plasma biomarker sample	X		
	Optional post-treatment biopsy		X	

Post-Study-Treatment Follow-Up Schedule of Activities

	Study Period	Post-Discontinuation Follow-Up		
		Short-Term Follow-Up ^a	Long-Term Follow-Up ^b	
	Duration	30 ± 5 days	60 ± 14 days	
	Visit	801	802-X	
Procedure Category	Procedure			Comments
Health Outcome Assessments	Worst Pain NRS, NFOSI-18	X		PRO instrumentation will be administered during the short term follow-up visit prior to extensive interaction with site staff.
Follow-Up	Survival assessment		X	Approximately every 90 (±14) days (telephone assessment is acceptable)

Abbreviations: CT = computed tomography; CTCAE = Common Terminology Criteria for Adverse Events; ECG = electrocardiogram; ECOG = Eastern Cooperative Oncology Group; NRS = numeric rating scale; NFOSI-18 = National Comprehensive Cancer Network – Functional Assessment of Cancer Therapy – Ovarian Symptom Index-18; NRS = numeric rating scale; PRO = patient-reported outcome; RECIST = Response Evaluation Criteria in Solid Tumors version 1.1 (Eisenhauer et al. 2009); SBO =small bowel obstruction.

- a Period begins the day after the decision that the patient will discontinue study treatment is made and lasts approximately 30 days.

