Planned hospitalizations or procedures for preexisting conditions that were recorded in the patient's medical history at the time of enrollment should not be considered SAEs. Hospitalization or prolongation of hospitalization without a precipitating clinical AE (for example, for the administration of study treatment or other protocol-required procedure) should not be considered SAEs.

Serious adverse events, including death, caused by disease progression should not be reported unless the investigator deems them to be possibly related to prexasertib.

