9.2.2. Suspected Unexpected Serious Adverse Reactions

Suspected unexpected serious adverse reactions (SUSARs) are serious events that are not listed in the IB and that the investigator identifies as related to study treatment or study procedure. United States 21 CFR 312.32 and Regulation (EU) No 536/2014 and the associated detailed guidances or national regulatory requirements in participating countries require the reporting of SUSARs. Lilly has procedures that will be followed for the recording and expedited reporting of SUSARs that are consistent with global regulations and associated detailed guidances.

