### **5.13.2. Adverse Events**

Adverse event (AE) verbatim terms will be provided by the investigators and then will be mapped by Lilly or its designee to corresponding terminology within the Medical Dictionary for Regulatory Activities (MedDRA) Lower Level term (LLT) dictionary. The investigator will use Common Terminology Criteria for Adverse Events (CTCAE) version 4.0 (NCI 2009) to assign AE severity grades.

Pre-existing conditions are defined as AEs that begin but do not resolve prior to the first dose of study drug in each study period. Pre-existing conditions will be presented by patient and can be combined with the listing of AE, so that the history of the pre-existing conditions/AEs can be traced.

A treatment emergent adverse event (TEAE) is defined as any AE that begins on or after the day of first dose in the reporting study period or any pre-existing condition that increases in CTCAE grade on or after the day of first dose in the reporting study period. The MedDRA LLT will be used in the treatment-emergent computation.

The number of patients who experienced a TEAE, or TEAE possibly related to study drug, will be summarized. Treatment-emergent adverse events will be summarized by SOC, by Preferred Term (PT) of decreasing frequency within SOC, and by maximum CTCAE grade and grade categories (any, Grade 3 or higher).

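### Protocol 9.2 defines a reasonable possibility of relatedness as an existing causal link; read literally, this can move merely suspected events to unrelated

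*Protocol*

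**What the plan says.** Protocol 9.2 has the investigator decide "whether or not an AE has a reasonable possibility of being related to study treatment or a study procedure", weighing the disease, concomitant treatments and other pathologies. The next sentence explains the key phrase: a reasonable possibility "means that there is a cause and effect relationship between the study treatment and/or study procedure and the AE". The paragraph before sets a softer task: "Investigators should record their assessment of the potential relatedness of each AE to study procedure or study treatment".

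Relatedness is then used in several places:

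- Protocol 9.2.2 defines SUSARs as "serious events that are not listed in the IB and that the investigator identifies as related to study treatment or study procedure".
- Protocol Table JTJN.3 (post-treatment follow-up) states: "After Visit 801, only study treatment-related serious events are to be reported".
- Protocol 9.2.1 uses the 9.2 phrase in adverb form for two groups: SAEs between consent and first dose (relation to study procedures only), and SAEs the investigator learns of after the patient has been discharged from the study.
- Protocol 9.2.1 also exempts SAEs and deaths caused by progression from reporting "unless the investigator deems them to be possibly related to prexasertib".
- Protocol 10.3.2 summarises AEs and SAEs by possible relationship to study drug. SAP 5.13.2 says that the number of patients with a "TEAE possibly related to study drug, will be summarized", and SAP 5.13.3 tabulates SAEs by relationship among other classifiers.

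**The concern.** The investigator's causality answer is a yes or no. If yes requires that a causal link exists, an honest investigator who only suspects the drug should answer no. The summaries headed possibly related would then hold only events judged to be caused by the drug, and a reader would take them for something wider.

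Safety and toxicity is a secondary objective, and the study has no concurrent control (protocol 5.4), so no comparison rate would reveal under-attribution. Protocol 3.2.2.3 reports fatal outcomes after sepsis or infection and after clinically significant bleeding. In pretreated patients with advanced cancer such events can have competing causes, so certainty about the drug will often be out of reach. The same holds for SUSARs, which by definition are not listed in the Investigator's Brochure.

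**Working it through.** No arithmetic applies. The plan gives no figure on this point, and the check is a reading of the definition against each place that relies on it.

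**Step 1: is the definition corrected anywhere?** The sentence in protocol 9.2 carries no qualifier such as may, suspected or possible. Protocol Appendix 1 has no entry for relatedness. SAP 5.13.2 and 5.13.3 use the term without defining it. Protocol 9.2 is therefore the only definition available.

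**Step 2: which uses inherit it?**

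| Place | Wording | Effect of the literal definition |
|---|---|---|
| Protocol 9.2.1, SAE before first dose | The defined phrase, for study procedures only | Carries over directly, but no drug has been given, so drug toxicity rates are not touched |
| Protocol 9.2.1, SAE learned of after discharge | The defined phrase | Carries over directly; a suspected-only event need not be notified |
| Protocol Table JTJN.3, after Visit 801 | Treatment-related, unqualified | Nothing softens it; a suspected-only SAE can go unreported |
| Protocol 9.2.2, SUSAR | Related, unqualified | Nothing softens it; the investigator may not identify a suspected-only event |
| Protocol 9.2.1, SAE put down to progression | Possibly related | Softer on its face; affected only if the site brings in the 9.2 definition |
| Protocol 10.3.2 and SAP 5.13.2 | Possible, possibly related | Softer on their face, but they depend on the investigator's recorded assessment under 9.2 and so reflect whichever standard the site used |

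**Step 3: what does not depend on relatedness?** All AEs after consent are recorded (9.2, 9.2.1). After first dose and while on study, any SAE goes to the sponsor within 24 hours, apart from the progression exemption (9.2.1). TEAEs are also summarised overall (SAP 5.13.2). The SAE tabulation uses relationship only as a classifier, and deaths during the study, within 30 days of treatment discontinuation, are summarised and listed with cause (SAP 5.13.3). Laboratory shift tables take no account of causality (SAP 5.13.4).

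**Step 4: what follows?** There are two different effects. For an on-study event not attributed to progression, the literal definition changes a label: the event is still recorded and tabulated but leaves the related subset, and if it is serious and unlisted the investigator may not identify it as a SUSAR. For an SAE after Visit 801 or after discharge, and possibly for one attributed to progression, the definition can decide whether it is reported at all.

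**Step 5: how large?** The related counts would fall in proportion to the share of suspected events in which the investigator is not satisfied that causation exists. The documents give neither that share nor a rate of suspected events. Any figure would only return the assumption put into it, so none is offered.

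**The case against.** The strongest reply is that the plan's intent is clear despite one careless sentence. The question itself asks about possibility. Weighing the disease and other treatments would make little sense if causation had to be established. Most of the later wording says possible or possibly. An experienced investigator may well apply that lower bar. For SUSARs, protocol 9.2.2 also refers to regulations and to sponsor procedures that are not reproduced, and these may catch what the investigator does not.

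Much of this stands, and it rules out three stronger readings:

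- A reader might infer that suspected events *are* classed as unrelated and *do* drop out. Nothing in either document instructs a site to code a suspected event as unrelated; it is a risk of literal application. Nor can SUSAR reporting be shown to fail, because the sponsor's procedures are not available.
- A reader might infer that on-treatment sepsis or bleeding would go unreported. Unless such an SAE is attributed to progression, it is notified whatever the causality call.
- A reader might infer that the progression clause contradicts itself. That clause says possibly related, and progression and drug can both contribute to one event. The contradiction appears only if the 9.2 definition is imported and a single cause is assumed.

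The reply does not remove the conflict. The gates in Table JTJN.3 and 9.2.2 have no softening word, and the post-discharge gate uses the defined phrase itself. Sites are left with two standards for one assessment, and the related tables may mix them. Sponsor procedures cannot recover an event that was never reported.

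**Conclusion.** The point holds as an internal inconsistency in an operative definition. It can lead to wrong classification if followed as written, and it should be corrected. The direction is known: too few events classed as related, fewer SUSARs identified by investigators, and some unreported SAEs where relatedness is the gate. The size is unknown. The conclusion assumes that at least some investigators apply the sentence in 9.2 literally; if all of them apply the possibly related standard, nothing is lost. The primary endpoint and the futility rules are not involved.

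**What to change.** In the defining sentence of protocol 9.2, replace *there is* with *there may be*, leaving the rest unchanged. Add a statement that this single definition governs related and possibly related in Table JTJN.3, 9.2.1, 9.2.2 and 10.3.2 of the protocol and in SAP 5.13.2 and 5.13.3, and align any CRF completion guidance with it.

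The change should go no further. A test such as *cannot reasonably be excluded* appears nowhere in the plan and is a different standard. In a single-arm study of pretreated patients it could class most events as related and make the related-TEAE table uninformative.

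The cost is one reworded sentence and a cross-reference. The downside is that somewhat more events will be classed as related and reported.
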